14.3.1 Recording and Reporting of AEs/SAEs

Information about all adverse events, whether volunteered by the subject, discovered by investigator questioning, or detected through physical examination, laboratory test or other means, will be collected and recorded on the Adverse Event eCRF

For this study, all AES/SAEs occurring from signed informed consent to week-16 study visit will be captured on the AE/SAE eCRF. Unless exempted as described above, all AEs/SAEs, whether or not deemed drug-related or expected, must be reported by the investigator or qualified designee within 1 business day of first becoming aware of the event. The investigator/qualified designee will enter the required information regarding the AE/SAE into the appropriate module of the InForm eCRF, which will automatically result in distribution of the information to Duke Clinical Research Institute Safety Surveillance (DCRI SS). If InForm is temporarily unavailable, the event, including the investigator-determined causality to study drug, should be reported via a paper back-up SAE form to DCRI SS. Upon return of the availability of EDC system, the AE/SAE information must be entered into the eCRF.

Follow-up

When additional relevant information becomes available, the Investigator will record follow-up information according to the same process used for reporting the initial event as described above. The Investigator will follow all reportable events until resolution, stabilization or the event is otherwise explained.

Investigators are also responsible for promptly reporting AE/SAEs to their reviewing IRB/EC in accordance with local requirements.

DCRI Safety Surveillance will follow all SAEs until resolution, stabilization, until otherwise explained or until the last subject completes the final follow-up, whichever occurs first. DCRI Safety Surveillance will report all SAEs to the Heart Failure Network trial team within 1-2 business day(s) of receipt and notify the Data Safety Monitoring Board (DSMB) chair monthly.

The DSMB will review detailed safety data approximately every 6 months throughout the study.

Suspected Unexpected Serious Adverse Reaction

AEs that meet the criteria of serious, related to study drug, and unexpected per investigator brochure or product labeling, qualify for expedited reporting to the regulatory authorities. DCRI will notify the FDA and all participating investigators in a written IND safety report of an SAR that is serious and is unexpected, based on the opinion of the investigator and DCRI safety medical monitor, as soon as possible, but not later than 15 calendar days after the event is confirmed to be a serious, unexpected SAR and qualifies for expedited reporting. DCRI will identify all safety reports previously filed with the IND concerning a similar SAR, and will analyze the significance of the SAR in light of the previous, similar reports. Follow-up reports will be sent to investigators to inform and update them about an important suspected adverse reaction if it significantly affects the care of the subjects or conduct of the study.

The site investigator will be responsible for reporting adverse events and unanticipated problems involving risks to subjects to their local IRBs/IECs in accordance with local regulations.

Day Zero

Day zero (0) is the calendar day that DCRI is first notified of an event. Day zero can also be the date the event qualified for expedited reporting as determined by the DCRI Safety Medical Monitor.

Pregnancy

Pregnancy occurring during a clinical investigation, although not considered a serious adverse event, must be reported to DCRI within the same timelines as a serious adverse event. The pregnancy will be recorded on the appropriate paper pregnancy tracking form. The pregnancy will be followed until final outcome. Any associated AEs or SAEs that occur to the mother or fetus/child will be recorded in the AE/SAE eCRF, within InForm.

15 STATISTICAL CONSIDERATIONS

15.1 Overview

A statistical analysis plan will be completed before the data are analyzed in a blinded fashion. All test statistics will be two-sided. Statistical tests with p-value <0.05 will be considered statistically significant. The trial results will be reported according to guidelines specified in the CONSORT statement. A flow diagram describing screening, recruitment, randomization, dropout, and vital status will be included in the primary manuscript. Adverse events and efficacy data will be presented by the two treatment groups. Adherence, dropout, and lost-to-follow-up will be carefully examined across the two treatment groups. All primary analyses will be based on intent-to-treat (ITT) principles using all randomized participants. Analyses will be performed using SAS software (SAS Institute, Inc, Cary, NC).

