4.3 Exploratory Objectives

1. To determine if the following subgroups of patients may derive differential benefit from oral Fe polysaccharide:

- 1) Patients with or without anemia. Anemia is defined as hemoglobin <12 g/dl.
- 2) Patients with or without venous congestion, based on the following criteria:
 - a) JVP>10cm
 - b) Lower extremity edema
- 3) Patients with and without an RER>1.1 during maximum incremental exercise
- 2. To determine change in renal function (creatinine, cystatin C) with iron polysaccharide vs. placebo
- 3. To determine if Fe repletion impacts markers of the RV-PV unit reserve capacity (i.e. VE/VCO2 slope) as assessed on CPET.
- 4. To determine if oral iron repletion influences clinical outcomes: time to death and HF hospitalization

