12 OUTCOME DETERMINATIONS

12.1 Primary Endpoint

1. Peak VO₂ (ml/min) as measured by CPET.

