12.2 Secondary Endpoints

- 1. O2 uptake kinetics and ventilatory efficiency as assessed by CPET
- 2. 6 Minute walk distance
- 3. Plasma NT-proBNP
- 4. KCCQ quality of life

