15.3 Analysis of Secondary and Exploratory Endpoints

Summaries of continuous variables will be displayed using the mean, standard deviation, median, and 25th-75th percentiles. For nominal variables, the number and percentages in each category will be presented. General linear models and nonparametric approaches will be used to analyze the continuous outcomes. For binary outcomes, Chi-square tests and Fisher's exact test will be used for unadjusted comparisons. For adjusted comparisons, logistic regression analysis will be used to compare oral Fe vs. placebo with the estimated odds ratio and associated 95% confidence interval.

For the composite exploratory endpoint of time to death and heart failure hospitalization, unadjusted time-to-event comparisons will be conducted using Kaplan-Meier survival estimates and log-rank tests. For adjusted analyses, Cox proportional hazards regression models will be used to estimate hazard ratios. Heart failure hospitalization is defined as an event that occurred primarily because of the documented presence of at least:

Clinical manifestations of worsening heart failure

• Use of additional or increased pharmacologic or mechanical interventions directed at the treatment of heart failure

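### Section 15.1 applies p<0.05 as the significance rule to every test, so across the five secondary measures the chance of at least one false positive is about 15-23% rather than 5% (minor)

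*Protocol*

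**What the plan says.** Protocol section 15.1 gives a general rule on testing: "All test statistics will be two-sided", followed by "Statistical tests with p-value <0.05 will be considered statistically significant". Neither sentence is restricted to the primary endpoint, and neither calls any p-value nominal or descriptive. The same section announces a separate plan: "A statistical analysis plan will be completed before the data are analyzed in a blinded fashion". That plan is not among the documents at hand.

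There is one primary endpoint (section 12.1: "Peak VO₂ (ml/min) as measured by CPET"), with one primary model in 15.2 and no interim efficacy analysis (15.4).

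Section 12.2 numbers four secondary endpoints. The first contains two measures: "O2 uptake kinetics and ventilatory efficiency as assessed by CPET". The others are "6 Minute walk distance", plasma NT-proBNP and KCCQ. For their analysis, 15.3 says: "General linear models and nonparametric approaches will be used to analyze the continuous outcomes". It names no lead method, no testing order and no adjustment.

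Section 15.5 gives power for secondary endpoints: above 90% for differences over 0.5 SD with more than 86 per group, and above 80% for differences over 0.43 SD.

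**The concern.** A protocol that is silent on secondary multiplicity may simply be leaving it to the SAP. Here the protocol fixes a threshold for all tests and calls any result below it statistically significant. If that is followed as written, each secondary measure is tested at the full 0.05, and no secondary claim depends on the primary result. A neutral result on peak VO₂ could then be reported beside a secondary benefit that is labelled statistically significant but is only a chance finding. At stake is the label attached to secondary results. The primary conclusion is not at risk.

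**Working it through.** **Inputs.** From the protocol: two-sided 0.05 per test (15.1); five secondary measures, from four numbered items with the first holding two (12.2); difference 1.0 and SD 2.0 ml/kg/min, 90% power, 86 per group, 20% missing data (15.5). Assumed: the correlation between secondary test statistics, which the protocol does not give. A common value of 0.3, 0.5 or 0.7 is used to show the range.

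**Step 1: reproduce the plan's own figures.** The standardised difference is d = 1.0/2.0 = 0.5.
- Normal approximation: n per group = 2(1.960 + 1.282)²/0.5² = 84.1, rounded up to 85. The t-test calculation gives 85.03, rounded up to 86, or 172 in total, as stated.
- Missing data: 86/0.8 = 107.5, rounded up to 108 per group, or 216 in total, which agrees with about 220.
- Secondary power with 86 per group at two-sided 0.05 (t-test): 90.3% at 0.5 SD and 80.1% at 0.43 SD. Both agree with 15.5.

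**Step 2: which significance level do the secondary power figures imply?** Splitting 0.05 equally over five measures (Bonferroni) gives 0.05/5 = 0.01 each. Power at 0.5 SD with 86 per group is then 74.9% (t-test). By the normal approximation, 0.5 × √(86/2) − 2.576 = 0.703, which gives 75.9%. So the figures in 15.5 match testing each secondary measure at the full 0.05, in line with the plain reading of 15.1, and do not match an equal split.

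**Step 3: chance of at least one false positive.** Suppose iron has no effect on any of the k measures and each is tested at 0.05.
- Independent tests: 1 − 0.95^k. For k = 5, 1 − 0.95⁵ = 22.6%. Counting only the four numbered items, 1 − 0.95⁴ = 18.5%.
- Upper limit under any dependence: k × 0.05. For k = 5 this is 25%.
- Correlated tests, k = 5, from simulation of equicorrelated normal statistics (400,000 draws):

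| Assumed common correlation | Chance of at least one false positive |
|---|---|
| 0.3 | 20.9% |
| 0.5 | 18.3% |
| 0.7 | 14.8% |

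These are roughly three times (14.8/5 = 3.0) to four and a half times (22.6/5 = 4.5) the nominal 5%. The expected number of false positives among the five is 5 × 0.05 = 0.25.

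**Step 4: the primary test.** One endpoint, one primary model and no interim efficacy look leave its type I error at 5%.

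**The case against.** The strongest reply is that multiplicity of secondary endpoints is ordinary SAP material and that the sentence in 15.1 is a generic statement of significance level. An SAP could compare adjusted p-values with 0.05, or use a fixed order, without plainly contradicting it. A fixed order also tests each step at the full 0.05, so the power figures in 15.5 rule out an equal split but not a sequence. This stands in part. The lack of an adjustment method in the protocol is not in itself a defect, and that is why the point is minor. It does not remove the point, because the rule as printed is unrestricted and any reader may apply it as it stands.

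Four stronger readings are tempting, and the documents do not support them.
- *A false positive is likely.* With five tests it cannot exceed 25%, so no false positive is the more probable result. Passing 50% takes 14 independent tests (1 − 0.95¹³ = 48.7%; 1 − 0.95¹⁴ = 51.2%).
- *There are seven or more secondary tests.* Adding week-8 tests of walk distance and KCCQ would give 1 − 0.95⁷ = 30.2%. Section 11.2 and Appendix A only schedule the collection of these data at week 8, and no section specifies a treatment comparison there. Nor does 15.3 clearly say that every outcome will be tested by both families of methods, and two tests of the same data would be strongly correlated.
- *Subgroups, renal markers and clinical events add to the family.* Section 4.3 already labels these exploratory, and the repeated-measures model in 15.2 is called a secondary analysis. Section 4.3 also contains an exploratory aim, "To determine if Fe repletion impacts markers of the RV-PV unit reserve capacity (i.e. VE/VCO2 slope) as assessed on CPET", beside the secondary endpoint of ventilatory efficiency. That is a labelling matter and does not change the count.
- *The trial's main conclusion would be overstated.* No section says that a secondary result will support an efficacy claim over a neutral primary, and 15.1 commits to CONSORT reporting.

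**Conclusion.** The point holds as a minor one. Section 15.1 declares significance at p<0.05 for all tests and does not confine this to the primary. If iron has no effect on any of the five secondary measures, the chance of at least one nominally significant result is 22.6% under independence, about 15-21% at assumed correlations of 0.7 to 0.3, and at most 25%, against a nominal 5%. The independence figure and the upper limit rest on the count of five and on the assumption of no effect on any of them. The middle range also rests on the assumed correlations. The primary type I error, sample size and power are not affected. An SAP with a testing order would settle the matter, but whether it has one cannot be seen here.

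**What to change.** Replace the general significance sentence in 15.1 with wording such as:

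> *The primary test is two-sided at 0.05. Secondary, subgroup and exploratory efficacy analyses are reported as estimates with 95% confidence intervals and nominal p-values and do not support confirmatory claims, unless the statistical analysis plan, finalised before unblinding, sets a fixed testing order that starts only after a significant primary result.*

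Two points go with it.
- Keep the wording to efficacy, so that the Fisher's exact comparisons of adverse events in 15.4 are left as they are.
- Add to 15.5 that the secondary power figures refer to a nominal, unadjusted 0.05.

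If a fixed order is chosen, each step needs one variable and one time point. For item 1 of 12.2 this means naming a single variable for each of its two measures.

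The cost is one passage in 15.1 and a short note in 15.5, with no loss of primary power and no change in sample size. The downside is that an isolated secondary p<0.05 can no longer be declared statistically significant. Under a fixed order, a measure placed late cannot be claimed once an earlier one fails.

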15.2 Analysis of the Primary Endpoint

A general linear model with the change in peak VO_2 measured at 16 weeks as the response variable and predictor variables including a treatment indicator and the baseline measure of peak VO_2 will be used in the primary analysis. The treatment effect will be determined by the point estimate and 95% confidence interval for the treatment indicator variable.

A secondary analysis of the peak VO₂ outcome will be conducted using a repeated measures analysis. For this analysis all measurement of peak VO₂(including baseline) will be treated as response variables. The following covariates will be included in the regression model treatment group, time period, treatment group * time period interaction, baseline VO₂ and baseline Fe level. An unstructured correlation matrix will be assumed for the repeated measures within subjects. The mixed model repeated measures analysis will be estimated using SAS PROC MIXED.

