8.7 Randomization, Stratification and Blinding

Randomization will be stratified by anemia status (anemia is defined as hemoglobin <12g/dL). A permuted block randomization method stratified by site will be used to ensure relatively equal distribution of subjects to each arm within each clinical site. Subjects will be randomized using procedures determined by the Coordinating Center (CC).

Blinding of the study, with respect to treatment groups will be preserved by the use of overencapsulation of Fe polysaccharide capsules. The Investigator may be asked at the end of the trial if he/she had obtained any information that may have led to the potential unblinding of treatment

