15.5 Sample Size Justification

The proposed sample size of 220 subjects will be adequate to address the primary objectives of the study. As in the HFN's PhosphodiesteRasE-5 Inhibition to Improve CLinical Status And

EXercise Capacity in Diastolic Heart Failure (RELAX) clinical trial, the assumed minimally important difference for peak VO₂ is 1.0 ml/kg/min. Based on prior studies within the HFN, a conservative estimate of 2.0 ml/kg/min for the standard deviation for peak VO₂ (ml/kg/min) will be assumed. Using a two-sample t-test a sample size of 172 subjects (86 per group) will provide 90% power to detect the minimally important difference. These calculations assume a common standard deviation of 2.0 ml/kg/min and a two-sided type I error of 0.05. Allowing for 20% missing data would result in a sample size of roughly 108 per group or a total sample size of approximately 220 subjects.

For secondary endpoints, a sample size of greater than 86 subjects per group will provide greater than 90% power to detect differences greater than 0.5 standard deviations for continuous endpoints. These calculations are based on the two-side t-test and assume that the data are normally distributed with a common standard deviation. Similar sample sizes will provide greater than 80% power to detect differences larger than 0.43 standard deviations.

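### The covariates named for the peak VO₂ models leave out both randomization factors (anemia status and site); if those factors are prognostic, the test is slightly conservative

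*Protocol*

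**What the plan says.** Protocol section 8.7 uses two factors in the allocation. The first is anemia: "Randomization will be stratified by anemia status (anemia is defined as hemoglobin <12g/dL"). The second is site: "A permuted block randomization method stratified by site will be used".

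Section 15.2 models change in peak VO₂ at 16 weeks with "predictor variables including a treatment indicator and the baseline measure of peak" VO₂. The result is read from that model: "The treatment effect will be determined by the point estimate and 95% confidence interval for the treatment indicator variable". The same section lists the covariates of the secondary repeated-measures model as treatment, time period, "treatment group * time period interaction, baseline VO₂ and baseline Fe level". Neither model names anemia status or site, although the second takes in baseline iron.

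The sample size in section 15.5 rests on an unadjusted two-sample t-test. It takes no credit for baseline or for stratification.

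**The concern.** Stratified allocation removes chance imbalance on the strata. If the strata are prognostic, the treatment estimate then varies less from trial to trial. A model without the strata leaves their contribution in the residual variance, so it reports a standard error suited to unstratified allocation. The estimate stays unbiased, but the confidence interval is wider than it need be and the test runs somewhat below its nominal level.

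What is at stake is efficiency and agreement between design and analysis. The choice is also better fixed in advance: covariates picked after unblinding invite dispute over a borderline p-value.

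**Working it through.** **Inputs from section 15.5:** "the assumed minimally important difference for peak VO₂ is 1.0 ml/kg/min"; the calculations "assume a common standard deviation of 2.0 ml/kg/min" and "a two-sided type I error of 0.05"; 86 evaluable per group for 90% power; 20% missing data. About 220 patients at about 20 sites are planned (section 9.4), allocated 1:1 (section 5.2).

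**The plan's own figure.** The normal approximation gives 85 per arm. The exact noncentral t gives 86 per arm with power 0.903. Allowing for missing data, 86/0.8 = 107.5, so 108 per arm or 216 in total, which the plan rounds to about 220. The stated size reproduces.

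**Assumption.** Let R² be the share of residual variance, after baseline peak VO₂, that anemia and site explain together. The documents give no value, so I take 0 to 10%, with 2.0 ml/kg/min as the residual SD before the strata are added.

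**Formulas at full balance within strata, 86 per arm:**
- SE reported by the listed model: 2.0 × √(2/86) = 0.305
- True SE: 0.305 × √(1 − R²)
- Ratio of reported to true SE: 1/√(1 − R²)
- Type I error of the listed model: 2 × [1 − Φ(1.96/√(1 − R²))]
- Power, listed model: Φ(1.0/true SE − 1.96/√(1 − R²))
- Power, strata in the model: Φ(1.0/true SE − 1.96)

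| R² | True SE | Ratio | Type I, listed | Power, listed | Power, strata added |
|---|---|---|---|---|---|
| 0 | 0.305 | 1.000 | 0.050 | 0.906 | 0.906 |
| 0.02 | 0.302 | 1.010 | 0.048 | 0.909 | 0.912 |
| 0.05 | 0.297 | 1.026 | 0.044 | 0.912 | 0.920 |
| 0.10 | 0.289 | 1.054 | 0.039 | 0.918 | 0.933 |

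The gain is 0, 0.3, 0.8 and 1.5 percentage points. With a noncentral t and degrees of freedom reduced for anemia and 19 site terms, the last column becomes 0.903, 0.908, 0.917 and 0.930.

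**Simulation, because blocks will often be incomplete.** If the two factors are crossed, 220/(20 × 2) = 5.5 patients fall in each cell on average. Settings: 220 patients, 20 sites, 172 evaluable, 4,000 replicates per scenario. Blocks of 4 within site by anemia and 35% anemia are assumptions, not figures from the protocol. Simulation error is about 0.005 for power (√(0.9 × 0.1/4000)) and about 0.0035 for type I error.

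| Variance explained | Power, listed model | Power, anemia fixed + site random |
|---|---|---|
| Anemia 0, site 0 | 0.898 | 0.900 |
| Anemia 5%, site 0 | 0.910 | 0.919 |
| Anemia 5%, site 5% | 0.905 | 0.923 |

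With neither factor prognostic, fixed site terms instead of a random intercept gave 0.885. At 5% each, the listed model reported a mean SE of 0.305 against a true SD of about 0.297; type I error was 0.039 for the listed model and 0.051 with the factors added.

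A separate simulation with the same assumed blocks and anemia prevalence, 20% missing data and 2,500 replicates per scenario compared the listed model with anemia plus fixed site terms:
- At R² = 0, adjustment did slightly worse: mean SE 0.309 against 0.302, power 0.896 against 0.911.
- At a total R² of 4% it gained nothing: mean SE 0.302 for both, power 0.911 against 0.912.
- At 10% it gained one point: power 0.928 against 0.918.

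Bias was about zero throughout. Type I error of the listed model was 0.038 to 0.052 across all scenarios, which ran up to R² = 20%.

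**The case against.** **The primary list is open.** Section 15.2 says the predictors *include* the two named terms, and section 15.1 leaves detail to an SAP that is not shown. This stands in part: the protocol does not rule the strata out. But the covariates of the secondary model are given as a definite list, which finds room for baseline iron and not for the randomization factors.

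**Nothing shows that the factors are prognostic.** This stands. A reader might infer that anemia was made a stratum because it was expected to predict response, but the protocol does not say so. Section 4.3 treats anemia as a possible modifier of benefit. Table 2.2 reports similar benefit above and below a hemoglobin of 12 in the largest earlier trial. Section 3.2 links iron-deficiency anemia to the level of peak VO₂, which the baseline term already covers in part. Site stratification is justified by even allocation alone. The loss is therefore conditional, and zero belongs in the range.

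**The size is easily overstated.** A reader might turn the SE ratio into lost patients: 172 × (1/(1 − R²) − 1) gives 9 at 5% and 19 at 10%. That confuses the reported SE with the real precision. Stratification has already secured most of the benefit: at a total R² of 10%, the simulated SD of the estimate was 0.291 without the strata and 0.290 with them (fixed site terms).

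**No trial objective is harmed.** This stands as well. At full balance the listed model has power 0.906 to 0.918 over the assumed range, and the simulated values agree with at least 90% within simulation error.

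**Conclusion.** The covariates named for both peak VO₂ models do not match the randomization factors. For R² between 0 and 10%, the model-based SE is 0 to about 5% too large, type I error is 5% down to about 3.9%, and roughly 0 to 2 percentage points of power are forgone. The R² range is an assumption. The closed-form figures also assume full balance within strata, and incomplete blocks would soften them.

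A reader might infer that the primary analysis is invalid or the trial underpowered. The documents support neither: there is no bias, the error is in the conservative direction, and the planned 90% power is kept. This is a free improvement of low severity.

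**What to change.** In section 15.2, add two terms to the primary model: the anemia stratum as recorded at randomization, as a fixed effect, and site as a random intercept. Add the same two terms to the secondary repeated-measures model of peak VO₂. Avoid about 19 fixed site terms, which can cost power if site is not prognostic; the random intercept showed no detectable cost in that case.

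The cost is one sentence of text, settled before unblinding. Both variables are already held in the randomization data, and the sample size does not change. If the SAP already contains these terms, it is enough to bring section 15.2 into line with it.

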17.3.2 Cardiopulmonary Exercise Testing Core Laboratory

Massachusetts General Hospital will serve as the core laboratory for cardiopulmonary exercise testing. Comprehensive site certifications will be performed for participating centers and CPETs will be electronically transferred to the MGH Core Laboratory. Detailed CPET procedures are outlined in the manual of operations.

Measurement Methods: The following procedures or measurements will be performed at various time points throughout the study (see Human Subjects for details). CPETs will be performed on each subject at baseline and 16 weeks. The lag in VO₂ increment following initiation of constant workload exercise, before steady state is reached, is the oxygen deficit (Fig 16.3.3).⁴⁵ Phase I of this period is a brief cardiodynamic phase that reflects increase in cardiopulmonary blood flow. The shallower phase II reflects O₂ extraction that we hypothesize is strongly influenced by Fe. The O₂ deficit will be measured as the time constant from the monoexponential equation: VO₂(t) = VO₂(baseline) + A(1-e^{-t/}r), where t is the time after the start of exercise, A is the amplitude of VO₂ response, and τ is the time constant.⁴⁶ Recovery O₂ kinetics (O₂ debt, denoted in **Fig 16.3.3**) correlate with recovery of energy stores as well as

blood and tissue O_2 stores after exercise.⁴⁷ Both O_2 deficit and debt are increased in HF and are related to symptoms during sub-maximum exercise.

Fig 16.3.3 O₂ kinetics during low level CPET

The CPET will also measure the primary endpoint, peak VO₂ and will consist of a 10 watt/min incremental load performed according to the HF Network CPET Core Lab Manual of Operations to derive the primary endpoint ΔpVO_2 , as well as VO₂ at AT and OUES.

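### The secondary repeated-measures model in Section 15.2 uses baseline peak VO2 as both response and covariate: with visit-specific variances it has no valid estimate, and with complete data it returns only the change-score difference

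*Protocol*

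**What the plan says.** Protocol Section 15.2 defines two analyses of peak VO2.

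- **Primary.** A general linear model for the change at 16 weeks, with "predictor variables including a treatment indicator and the baseline measure of peak VO_2 will be used in the primary analysis". This is an ordinary ANCOVA.
- **Secondary.** "A secondary analysis of the peak VO₂ outcome will be conducted using a repeated measures analysis". For its outcome the text reads: "For this analysis all measurement of peak VO₂(including baseline) will be treated as response variables". Its covariates are "treatment group, time period, treatment group * time period interaction, baseline VO₂ and baseline Fe level". On the covariance it says: "An unstructured correlation matrix will be assumed for the repeated measures within subjects". PROC MIXED is named as the procedure.

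Section 17.3.2 fixes the measurement times: "CPETs will be performed on each subject at baseline and 16 weeks". The schedule in Appendix A agrees. There is thus one post-baseline value per participant.

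**The concern.** A baseline measurement can enter a longitudinal model as a response or as a covariate. Here it is explicitly both. The explicit inclusion of baseline among the responses rules out the charitable reading in which only the post-baseline value is modelled. The covariate list also has no baseline-by-time term, so one slope must serve both visits.

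At stake is the usefulness of a pre-specified supporting analysis of the primary endpoint. Depending on how the covariance is read, it either has no maximum-likelihood solution or reproduces an unadjusted change-score comparison under the name of a mixed model. In the second case a reader could take it as corroboration of the ANCOVA when it is a less precise version of the same comparison.

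**Working it through.** **Inputs.** From Section 15.5: difference 1.0 ml/kg/min, SD 2.0 ml/kg/min, "a two-sided type I error of 0.05", 86 per group. From Sections 15.2 and 17.3.2: the model terms and the two visits. Assumed: the baseline to week-16 correlation rho (not given in the protocol), and SD 2.0 at each visit.

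**Plan's own figure.** The noncentral t distribution gives power 0.8999 at 85 per group and 0.9032 at 86, so 86 per group (172) is reproduced. With 20% missing, 86/0.8 = 107.5, or 108 per group and 216 in total, stated as about 220. Nothing below changes this.

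**Step 1: the model as written.** For participant i with arm T, baseline value B and iron level F:

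- baseline row: Y0 = m + a·T + b·B + g·F + e0
- week-16 row: Y1 = m + a·T + t + d·T + b·B + g·F + e1

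Here B is Y0. Setting b = 1 and m = a = g = 0 makes every e0 exactly zero.

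**Step 2: visit-specific variances.** With zero baseline residuals, the log-likelihood contains −(N/2)·ln(v0), where v0 is the baseline residual variance. It grows without limit as v0 goes to 0. With N = 172, each tenfold fall in v0 should add (172/2)·ln 10 = 198.0. In one simulated trial (86 per arm, rho 0.7, true effect 1.0):

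| Baseline residual variance | ML log-likelihood | REML log-likelihood | Slope on baseline | Treatment × time |
|---|---|---|---|---|
| 1 | −133.0 | −149.7 | 0.946 | 1.1102 |
| 0.01 | 263.0 | 237.1 | 0.995 | 1.1102 |
| 0.000001 | 1055.1 | 1010.8 | 0.99995 | 1.1102 |

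The ML rise over six tenfold steps is 1055.1 + 133.0 = 1188.1, which matches 6 × 198.0. A free optimiser ran to a baseline variance of 3e-23 and a week-16 variance of 1.6e6. The standard error of the contrast was 0.217 with the residual correlation held at 0, and 0.759 along the REML profile. It therefore depends on where the search stops.

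**Step 3: one common variance, free correlation.** On the same data this converged: slope 0.860, treatment × time 1.1102, SE 0.217.

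**Step 4: what the contrast is.** The terms b·B and g·F are the same in both rows of a participant, so they cancel from week 16 minus baseline. With complete data and a free mean for each arm and visit, d is exactly the difference between arms in mean change. The simulated trial confirms it: the raw change-score difference is 1.1102 (SE 0.217), against 1.1191 (SE 0.201) from ANCOVA.

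**Step 5: cost in precision.** With equal variances at the two visits, the variance per participant is 2·SD²·(1−rho) for the change score and SD²·(1−rho²) for ANCOVA. The ratio is 2/(1+rho) and does not involve the SD. Standard errors multiply by 2/86 and take the root. At rho 0.7, for example, √(2.4 × 2/86) = 0.236 and √(2.04 × 2/86) = 0.218.

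| rho (assumed) | SE change score | SE ANCOVA | Variance ratio |
|---|---|---|---|
| 0.5 | 0.305 | 0.264 | 1.33 |
| 0.7 | 0.236 | 0.218 | 1.18 |
| 0.9 | 0.136 | 0.133 | 1.05 |

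**Step 6: missing week-16 values.** The identity in Step 4 then no longer holds exactly. Two sets of simulations, with missingness that depends on baseline (an assumption), show this:

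- About 28% missing: the estimate moved from 1.22 to 1.14 according to where the variance was held, against 1.31 from ANCOVA.
- About 21–23% missing, common-variance reading: 0.874, 0.929 and 1.162, against change-score values of 0.879, 0.880 and 1.182.

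**The case against.** The strongest reply has four parts.

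- **The text says correlation matrix, not covariance matrix.** Taken literally, with one common variance, the model can be fitted (Step 3). This stands, and it limits the unbounded likelihood to the visit-specific reading. That reading is the usual one for an unstructured matrix, and the literal one still yields only the change-score contrast with complete data.
- **The model is secondary.** The primary ANCOVA, its confidence interval and the sample size do not depend on it. This stands in full.
- **The precision loss is modest.** It is 5% in variance at rho 0.9, and a change-score estimate is less efficient rather than misleading. This stands; the size turns on a correlation that the protocol does not give.
- **The repaired model is barely more independent of the ANCOVA than the current one.** This is largely true with a single post-baseline visit. The case for repair is that a pre-specified model should be estimable and no less precise than the primary, not that it would supply new evidence.

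A reader might go further and infer that PROC MIXED will fail and that a substitute will be chosen after unblinding. The documents do not support that. The procedure was not run, so its exact behaviour is a prediction. Section 15.1 also has a statistical analysis plan completed before the data are analysed, which leaves room for correction. Nor can it be said that this is the only supporting analysis, because that plan is not shown.

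**Conclusion.** The specification error is real and stands in the protocol's own words: baseline peak VO2 is a response and a covariate in one two-visit model. With visit-specific variances the likelihood has no maximum, which is algebra and does not depend on simulation settings. With a common variance the model can be fitted. Under both readings, complete data give the raw change-score difference. The resulting loss in variance runs from 5% to 33% over assumed correlations of 0.9 to 0.5, taking equal variances at the two visits. With missing week-16 values, the result also depends on the fitted variances and can drift from ANCOVA; how far depends on the missingness pattern.

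This should be fixed, but it is not a threat to the trial's main inference.

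**What to change.** In Section 15.2, and correspondingly in the statistical analysis plan:

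- Remove baseline VO2 from the covariates of the repeated-measures model.
- Keep baseline and week-16 peak VO2 as responses, with an unstructured covariance.
- Constrain the arms to a common baseline mean: a time effect, plus a treatment effect at week 16 only. Deleting the covariate alone is not enough, because with a treatment main effect kept the interaction is still the change score.
- Baseline Fe may stay. Adding the randomization factors is optional.

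This model has about ANCOVA precision: in a separate simulated trial (n = 176, rho 0.7) it gave 1.121, against 1.119 from ANCOVA and 1.156 from the change score. It also takes in participants with no week-16 CPET, although with one later visit they add little to the treatment contrast itself.

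The alternative is to keep baseline VO2 as a covariate, make week 16 the only response, and state that this is the primary ANCOVA with baseline Fe added.

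Either change costs about two sentences and needs no further data and no extra patient visits.
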